The study will start after the protocol is approved by the EMA, and CAB+RPV LA is registered and commercially available in the relevant countries and is expected to continue through 2026 or later, for a total of five years of study period. Annual interim reports with cumulative data will be submitted and a final report is expected to be submitted in September 2026.

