5. MILESTONES

Milestone	Planned date
Draft Protocol Submission	Dec 31, 2020
Study Start (Protocol Approval)	Estimated - June 2021
1st Interim Report	Draft -Dec, 2022
_	Final- Mar, 2023
2 nd Interim Report	Draft -Dec, 2023
	Final- Mar, 2024
3 rd Interim Report	Draft -Dec, 2024
	Final- Mar, 2025
4 th Interim Report	Draft -Dec, 2025
	Final- Mar, 2026
Data Collection Completion	June 2026 or 5 years following
_	commercial availability of CAB
Final Report	Sep 2026
Supplemental Report	Depends on when the last individual
_	discontinuing the CAB+RPV LA
	regimen completes 4-years of follow up

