8.2. Study Population and Setting

Study Population:

The study population will include PLWH over the age of 18 years, from EuroSIDA clinical sites who are new users of CAB and/or RPV LA containing regimens over a period of 5 years. Persons will be eligible for inclusion from the date of starting the treatment regimens after approval and commercial availability of the regimens. Only the first exposure to CAB and/or RPV LA containing regimens will be included in the primary analyses.

The potential regimen combinations are listed below (Note that CAB+RPV LA is the only approved regimen):

- a. CAB+RPV LA regimen only
- b. CAB LA monotherapy
- c. CAB LA use in combination with ARVs other than RPV LA
- d. RPV LA monotherapy
- e. RPV LA use in combination with ARVs other than CAB LA
- f. CAB LA+RPV LA+other ARVs
- g. Combined group b-f

EuroSIDA Cohort description:

The EuroSIDA study was initiated in 1994 and is a prospective observational cohort study of more than 22,000 individuals followed in over 100 hospitals in 34 European countries, and Israel and Argentina. The main objective of the study is to assess the impact of ARV drugs on the outcome of the general population of PLWH living in Europe.

In EuroSIDA, annual data collection is performed directly from clinics on individuals using comprehensive standardized clinical record forms via REDCap or electronic data transfer using the HICDEP format that includes information on outcomes and covariates [2]; further information is available at https://www.hicdep.org/. For each person, the date of starting and stopping each ARV drug is recorded. ATC codes for all ARVs and most non ARVs are collected. Dates of diagnosis of all AIDS defining diseases are recorded, using the 1993 clinical definition of AIDS from the Centers for Disease Control and Prevention. All EuroSIDA data undergo extensive data checks, queries and central clinical event validation to ensure a high quality and completeness of data.

Table 1. EuroSIDA currently contributing countries and geographical regions

Southern	Central Western	Northern Europe	Central Eastern	Eastern
Europe	Europe		Europe	Europe
Spain	France	United Kingdom	Poland	Estonia
Portugal	Belgium	Ireland	Czech Republic	Lithuania
Italy	Luxembourg	Netherlands	Bosnia-Herzegovina	Belarus
Greece	Switzerland	Denmark	Hungary	Ukraine
	Austria	Sweden	Romania	Russia
	Germany	Norway	Serbia	Georgia
		Finland	Slovenia	
		Iceland	Croatia	
*Israel			Albania	
*Argentina			North Macedonia	

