8.3.2. Outcome definitions

1.Regimen discontinuations: Discontinuation of CAB+RPV LA regimen for any reason during the study period will be captured, tabulated and reported.

Individuals who receive the oral lead-in but never initiate the CAB+RPV LA regimen will be tabulated separately but not included in the primary analysis.

Discontinuation of CAB +RPV LA will be defined as the latest date of the next scheduled injection which is missed and where bridging therapy has not been started. For example, for monthly dosing, if the first injection of CAB+RPV LA was received on June 1st, the second injection should be received on July 1st (allowed time window for second injection is June 24th to July 8th). The third injection should follow the timing of the first injection and should be received on August 1st (allowed time window for third injection is July 25th to August 8th). If not, date of discontinuation will be defined as August 8th (Monthly dosing).

For every 2 month dosing, if the first injection of CAB+RPV LA was received on June 1st, the second injection should be received on July 1st (allowed time window for second injection is June 24th to July 8th). The third injection should follow the timing of the first injection and should be received on September 1st (allowed time window for third injection is August 25th to September 8th). If not, date of discontinuation will be defined as September 8th (Every 2 month dosing).

Discontinuation will also be captured, tabulated and reported for any other CAB and/or RPV containing regimen.

Durability will be measured as proportion of individuals continuing on the regimen at the end of 6, 12 and 24 months.

Adherence will be assessed by estimating the number of individuals that missed one or more consecutive injections without taking daily oral bridging therapy or any other oral ARV regimen while not on CAB+RPV LA regimen and mean and median number of injections missed during a 12-month period. We will also estimate the number who received the injections seven or more days later than their scheduled injection visit and median duration of delayed injections in persons using bridging therapy.

In the standard follow-up data collection in EuroSIDA reasons for discontinuation are recorded as below.

Table 3. EuroSIDA – Reasons for Treatment Discontinuation

Code	Reason for Stopping Treatment
1	Treatment failure (i.e. virological, immunological, and/or clinical failure
1.1	Virological failure

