8.3.3. Confounders and effect modifiers

The study will examine the effect of potential confounders and effect modifiers as shown in Table 2 above on the risk for outcomes of interest.

Demographic variables

- Age
- Sex
- Route of HIV Infection
- Number of years since HIV diagnosis
- Ethnic origin
- Geographic region
- Date of ART initiation

Date CAB and/or RPV LA started

Virologic variables at regimen initiation

- HIV VL at initiation of CAB LA and/or RPV LA containing regimens (and in the 12 months prior to regimen start)
 - o Continuous (copies/mL)
 - o Categorical:
 - <50 copies/mL (or < LOD in clinics where LOD > 50 copies/mL)
 - $\ge 50 \text{ to } < 200 \text{ copies/mL}$
 - $\ge 200 \text{ to } < 10,000 \text{ copies/mL}$
 - \geq 10,000 to <100,000 copies/mL
 - \geq 100,000 copies/mL

Immunologic variables at regimen initiation

- CD4 cell count at initiation of CAB LA and/or RPV LA containing regimens (and in the 12 months prior to regimen start)
 - Continuous (cells/μL)
 - o Categorical:
 - CD4 \geq 500 cells/ μ L
 - CD4 count \geq 350 to <500 cells/ μ L
 - CD4 count <350 cells/µL
- CD4 nadir prior to initiation of CAB LA and/or RPV LA based ARV regimens

Clinical variables at regimen initiation

- HIV Subtype where available
- History of previous use of integrase inhibitor-based or NNRTI-based regimen
- History of previous antiretroviral exposure
- History of previous virologic failure
- History of previous HIV drug resistance and any historical HIV-1 subtype information, where available
- Body Mass Index (BMI), height, weight
- History of AIDS-defining Events (ADE)
- Concurrent medications (Etravirine, Rifampicin, Rifapentine, Rifabutin, Ribavirin, Ketoconazole, Fluconazole, Itraconazole, Clarithromycin, Erythromycin and other medications where data are available)
- Comorbidities (all defined to be consistent with published EuroSIDA analyses)
 - o HCV co-infection [3]
 - o HBV co-infection [4]
 - o End Stage Liver Disease (ESLD) (hepatocellular carcinoma, ascites, hepatorenal syndrome, grade III/IV hepatic

- encephalopathy, unspecified liver decompensation, oesophageal variceal bleeding, liver transplantation) [3]
- Cardiovascular Disease (CVD) (myocardial infarction, stroke, invasive coronary procedure) [3]

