Non-adherence to dosing schedule will be assessed by estimating the number of individuals that missed one or more consecutive injections without taking daily oral bridging therapy or any other oral ARV regimen while not on CAB+RPV LA regimen and median number of injections missed during a 12-month period. We will also estimate the number who received the injections seven or more days later than their scheduled injection visit and median duration of delayed injections in persons using bridging therapy. In addition, the number of individuals who missed one or more consecutive injections without taking daily oral bridging therapy or those who received the injections seven or more days later than their scheduled injection visit will be assessed and patient characteristics for those individuals that are non-adherent will be described.

Logistic regression will be used to identify factors associated with not starting CAB+RPV LA in those that start lead in, to compare those missing injections where bridging treatment is used, non-adherence and to identify factors associated with discontinuation of CAB+RPV LA (when there are more than 30 endpoints). Potential explanatory variables are listed above. The model building strategy will follow EuroSIDA protocol and include variables significant in univariate analyses as well as *a priori* pre-specified variables of interest.

AIM 3. Assess the clinical effectiveness (i.e. proportion individuals experiencing virologic failure and proportion with undetectable VL) among PLWH who initiate CAB+RPV LA regimen

The study will estimate the proportion with virologic failure during the first six months and at six, twelve and twenty four months after the start of the treatment with injectable regimen. Given that this study involves persons in routine clinical care, and who may not attend clinic appointments at 6, 12 or 24 months, a window of 12 weeks around the date in question will be used for virologic failure. Thus, the proportion with virologic failure during first six months, at 6, 12 or 24 months \pm 6 weeks will be used; and if none is available, the first measurement during first six months, after 6, 12 or 24 months (and at most 6 weeks after the measurement).

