Descriptive analyses will compare those with and without virologic failure to assess any differences in baseline characteristics of the two groups. Detailed analysis of additional risk factors will be limited to persons with 6, 12 or 24 months of follow-up. Multivariable logistic regression models will investigate the factors associated with virologic failure at 6 months, 12 months and 24 months after CAB+RPV LA initiation. Potential explanatory variables are listed above. We will also investigate the impact of missed doses and use of oral bridging therapy by using the data collected via the CRF. Multivariate analyses will be performed when > 30 persons on CAB+RPV LA have virologic failure and analyses will be limited to persons with > 6-, 12- or 24-months follow-up. The model building strategy will follow EuroSIDA protocol and include variables significant in univariate analyses as well as *a priori* pre-specified variables of interest. Primary analysis for clinical effectiveness will include individuals on CAB+RPV LA, with VL of <50/copies/mL at regimen initiation. In addition, all the analyses will be conducted separately for individuals on CAB+RPV LA with VL of ≥50 copies/mL at regimen initiation.

Our primary analyses of virologic outcomes will censor follow-up at discontinuation of CAB+RPV LA, last visit or death, whichever occurs first, an on-treatment approach to analysis. Sensitivity analyses will use an intent to treat approach and virologic outcomes will be assessed regardless of regimen discontinuation.

We will perform additional sensitivity analysis limited to those who start CAB+RPV LA with resistance data available, to confirm no present or past evidence of viral resistance to, and no prior virological failure with agents of the NNRTI and INSTI class.

AIM 4. Monitor for resistance and next treatment response among individuals who switched off CAB+RPV LA regimen

Monitoring for resistance

Since this is a non-interventional study aiming to capture individual care in real world setting, the study will not mandate resistance testing following discontinuation of the regimen of interest. Health care providers following the local treatment guidelines decide

what laboratory and resistance tests are to be conducted. Data thus generated will be captured and analyzed by the study team.

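### Aim 2 models discontinuation of CAB+RPV LA by logistic regression with no time horizon, so start date (and region, if launches are staggered) can look like a risk factor only because follow-up differs

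*Protocol*

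**What the plan says.** Section 8.6, Aim 2, names logistic regression "to identify factors associated with discontinuation of CAB+RPV LA (when there are more than 30 endpoints"). The event count is the only condition attached. Candidate covariates come from section 8.3.3, and the model keeps those significant univariately plus pre-specified ones. The 8.3.3 list includes geographic region and "Date CAB and/or RPV LA started".

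Section 8.3.2 defines the outcome without a horizon: "Discontinuation of CAB+RPV LA regimen for any reason during the study period will be captured, tabulated and reported". The same section measures durability as the proportion still on the regimen at 6, 12 and 24 months, but the regression is not tied to those points.

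Section 8.2 enrols "new users of CAB and/or RPV LA containing regimens over a period of 5 years". Section 5 ends data collection at "June 2026 or 5 years following" commercial availability. Before that, "Annual interim reports with cumulative data will be submitted" (section 3), so the model may be run at several cuts, each with unequal follow-up.

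Aim 3 is handled differently. Virologic failure is modelled at 6, 12 and 24 months, and "analyses will be limited to persons with > 6-, 12- or 24-months follow-up".

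**The concern.** Discontinuation accumulates with time. When entry is staggered and the close is common, time at risk is the gap between start date and data cut, here from near zero to about five years. A yes/no model that ignores this gap attributes its effect to any covariate correlated with it. Start date is the extreme case, because at a given cut it determines potential follow-up exactly. Region is affected as well if the regimen reaches some regions later than others.

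The risk is that a post-authorisation study reported to regulators says later starters persist better, or that some regions stop less, when the stopping rates are the same. The univariate screen makes it likely that start date is retained.

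**Working it through.** The protocol gives no figure for this model and no annual discontinuation rate, so there is nothing to reproduce. Inputs from the protocol are entry over 5 years (8.2), close at about 5 years (section 5), N = 500 as one of the Table 4 sizes (8.4), and CRF injection capture to 24 months plus six weeks, about 2.115 years (Annex 1). Assumptions are a constant hazard h of 0.10 per year (range 0.05 to 0.20), uniform entry, and no true effect of any factor.

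**1. Follow-up alone.** P(stopped by t) = 1 − exp(−ht). At h = 0.10:
- 0.5 y: 4.9%; 1 y: 9.5%; 4 y: 33.0%; 4.5 y: 36.2%.
- Odds ratio, 4.5 v 0.5 y: (0.362/0.638)/(0.049/0.951) = 11.1 from unrounded values (10.0 to 13.9 over the hazard range).
- Odds ratio, 4 v 1 y: 4.7 (4.3 to 5.5).
- If the longer follow-up is capped at 2.115 y: 4.6 against 0.5 y and 2.2 against 1 y.

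**2. Start date as covariate.** Simulated studies with N = 500, entry uniform over 5 years, h = 0.10:
- Uncapped: odds ratio about 0.60 per later year, p < 0.05 in about 100%.
- Capped at 24 months plus six weeks: about 0.77, p < 0.05 in about 86% (repeat runs differ by a point or two).

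In a variant where 40% of people enter only from year 2, hazards of 0.05 to 0.20 gave odds ratios of 0.61 to 0.53 uncapped (at least 99.7% significant) and 0.74 to 0.70 capped (72% to 99.8%).

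**3. Region, if launch timing differs.** For follow-up uniform on 0 to b, P = 1 − (1 − exp(−hb))/(hb). At h = 0.10:
- b = 5: 1 − 0.3935/0.5 = 21.3%.
- b = 2 (three-year launch lag): 1 − 0.1813/0.2 = 9.4%.
- Odds ratio: (0.213/0.787)/(0.0937/0.9063) = 2.6.
- With the cap c = 2.115, the early region has P = 1 − [(1 − exp(−hc))/h + (5 − c)exp(−hc)]/5 = 15.2%. The late region stays at 9.4%, so the odds ratio is 1.7.

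False-positive rates with 250 people per region:

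| Assumed lag | Uncapped | Capped |
|---|---|---|
| 3 years | 96% | 49% |
| 1 year | 18% | 6% |

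With identical entry patterns in both regions (separate runs, N = 500, uncapped) the region odds ratio is 0.99 and p < 0.05 in 6%, which is close to nominal.

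**4. The alternatives.** Under the same null, a rate model with a log person-time offset and a logistic model at 12 months among people with at least 12 months of potential follow-up both find a region effect in about 3 to 5% of runs when one region enters late, with or without the cap.

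**The case against.** - **Only the horizon is unstated.** The protocol never says ever-discontinued. The phrase about the study period governs capture and tabulation, and an SAP could tie the model to the durability time points. The wording point is fair. But the protocol does choose a binary model for a time-dependent event, makes an event count its only condition, and sets horizons in Aim 3 but not here. As written, the rule ignores time at risk.
- **Follow-up may not reach five years.** Annex 1 collects injections only to 24 months plus six weeks, and a missed scheduled injection defines discontinuation. This stands and shrinks the effect, so both versions are shown above. Routine ARV stop dates (8.3, Table 2) continue beyond the cap, and even capped the start-date artefact remains in most runs. The reporting lag in 8.5.2 moves the cut but does not make follow-up equal.
- **The region effect rests on assumptions.** This stands. No launch dates are given. With a one-year lag and capped data, false positives are near nominal. If stopping is front-loaded (Weibull shape 0.5, same one-year risk), the three-year-lag rates fall to 38% uncapped and 19% capped. With 100 per region only about 100 × (0.213 + 0.094) = 31 events are expected, so the trigger may not be met. Adjusting for start date also removes the region artefact, leaving only start date's own coefficient.
- **The model is minor.** Objective 2 lists proportions, reasons and non-adherence, not factors for discontinuation, and Annex 2 says no hypotheses are tested. This stands and lowers the severity.

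A reader might infer that any predictor found would be false, or that dosing schedule and clinic are affected. The documents do not support this: factors unrelated to entry time are not biased, and neither of those two variables is in the 8.3.3 list.

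**Conclusion.** The point holds for the discontinuation model in Aim 2. As specified, start date will appear protective for later starters even when nothing differs: an odds ratio of about 0.60 per year and nearly certain significance, or about 0.77 and 86% with capped data, at N = 500 and a constant 10% per year. Those sizes depend on the assumed hazard and uniform entry; the direction depends only on staggered entry to a common close. Region is a conditional concern that needs launch dates to differ materially. Fixed-time durability, reasons for stopping and the Aim 3 models are untouched. Severity is should-fix: a secondary model, run only above 30 events, but one whose stated method gives a predictable artefact for a listed covariate.

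**What to change.** In 8.6, Aim 2, replace the discontinuation model with one of the following:

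- **Fixed horizon.** Logistic regression for discontinuation by 6, 12 and 24 months, among people whose first injection was at least that long before the data cut. The restriction must use potential follow-up. Restricting on time actually spent on the regimen would remove the early discontinuers, who are the events.
- **Person-time.** A Cox or Poisson model from first injection, using all starters.

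In either case, state whether death and loss to follow-up, both listed as discontinuation reasons in Table 3, count as events or are censored. Keep the trigger of more than 30 events, and say whether injection data to 24 months plus six weeks or routine stop dates define the outcome.

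The cost is a few sentences. Start and stop dates are already collected, and last visit is already used for censoring in Aim 3. The fixed-horizon version loses recent starters. Under uniform entry it keeps 90%, 80% and 60% of them at 6, 12 and 24 months. With N = 500 and 10% per year that is about 450 × 0.049 = 22, 400 × 0.095 = 38 and 300 × 0.181 = 54 events, against 500 × 0.213 = 107 for an uncapped person-time model. The 6-month model might therefore not reach the trigger.

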8. RESEARCH METHODS

8.1. Study Design

A prospective observational cohort study nested within the EuroSIDA study, using data from individual medical records from participating clinical sites will be conducted over a period of five years to meet the study objectives.

This study will be conducted through collaboration with EuroSIDA, a well-established, prospective observational cohort study of more than 13,000 individuals under active follow up in over 100 hospitals in 34 European countries, and Israel and Argentina [1].

For this non-interventional study, treatment and laboratory testing decisions will be made by the treating physician according to standard practice, taking into account the treatment history, individual characteristics, the approved SmPc for CAB+RPV oral and LA

formulations, contemporary regimen and local guideline or recommendations. All individuals who discontinue the regimen for any reason, will be followed for up to 48 months after discontinuation. The study protocol will be implemented by the EuroSIDA coordinating center.

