2. Clinical effectiveness: Primary analysis for clinical effectiveness will include only those initiating the regimen per label i.e. initiating CAB+RPV LA with VL<50 copies/mL at regimen initiation. The following VL measures will be used for effectiveness assessment:

- 1. Proportion of individuals, virologically suppressed/undetectable (<50 copies/mL) at 6, 12 and 24 months following initiation of CAB+RPV LA regimen
- 2. Proportion of individuals with VL <200 copies/mL at 6, 12 and 24 months following initiation of CAB+RPV LA regimen
- 3. Proportion of individuals with confirmed virologic failure (CVF) during the first 6 months, and at 6, 12 and 24 months following initiation of CAB+RPV LA regimen defined as:
 - Two consecutive HIV RNA VL levels ≥200 copies/mL or
 - One HIV RNA VL level ≥200 copies/mL and regimen discontinuation within 4 months of VL ≥200 copies/mL

3. Resistance Testing:

Since this is a non-interventional study aiming to capture individual care in real world setting, the study will not mandate resistance testing following discontinuation of CAB+RPV LA regimen. Health care providers following the local treatment guidelines decide what laboratory and resistance tests are to be conducted. Data thus generated, including available HIV-1 subtypes, will be captured and analyzed by the study team.

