Descriptive analyses will compare those with and without virologic failure to assess any differences in baseline characteristics of the two groups. Multivariable logistic regression models will investigate the factors associated with virologic failure at 6 months, 12 months and 24 months after regimen initiation. We will also investigate the impact of missed doses and use of oral bridging therapy by using the data collected via the CRF Multivariate analyses will be performed when > 30 persons on the regimen of interest have virologic failure and analyses will be limited to persons with > 6-, 12- or 24-months follow-up.

Depending on the numbers, additional analysis stratifying by VL at regimen initiation (<50 copies/mL and ≥50 copies/mL) will be conducted. We will perform additional sensitivity analysis limited to those who start one of the other regimens with resistance data available, to confirm no present or past evidence of viral resistance to, and no prior virological failure with agents of the NNRTI and INSTI class.

Completeness of data

Not all variables within EuroSIDA are complete for all persons; missing data is rarely missing at random from observational cohort studies. Data may be categorized, including a category for missing, persons may be completely excluded with missing data, or imputation can be used. None of these approaches is likely to be unbiased, but with a small number of primary endpoints anticipated, excluding those with missing data would not be a reasonable approach to analysis.

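### The Aim 3 fallback for people with no viral load at 6, 12 or 24 months lies inside the ±6-week window, and no stated analysis shows how much these people matter

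*Protocol*

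**What the plan says.** Protocol section 8.3.2 lists two single-measurement outcomes: "Proportion of individuals, virologically suppressed/undetectable (<50 copies/mL) at 6, 12 and 24 months following initiation of CAB+RPV LA regimen" and "Proportion of individuals with VL <200 copies/mL at 6, 12 and 24 months following initiation of CAB+RPV LA regimen". It gives neither a window, a denominator nor a category for people without a result. Confirmed virologic failure is the third outcome.

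In section 8.6, the Aim 3 heading covers both "proportion individuals experiencing virologic failure and proportion with undetectable VL". The timing rule names failure only: "a window of 12 weeks around the date in question will be used for virologic failure", spelled out as ±6 weeks. If no value is available, the rule takes "the first measurement during first six months, after 6, 12 or 24 months (and at most 6 weeks after the measurement"). The parallel rule in Aim 4 (12 to 48 months after stopping) also has ±6 weeks and a later-measurement fallback, but without the 6-week cap.

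On who contributes a result:
- Section 8.1: "treatment and laboratory testing decisions will be made by the treating physician according to standard practice".
- Section 8.6, Aim 3: the primary analyses "censor follow-up at discontinuation of CAB+RPV LA, last visit or death, whichever occurs first". The intent-to-treat sensitivity analysis assesses virologic outcomes whether or not the regimen was stopped. The risk-factor models are limited to people with enough follow-up.
- Section 8.6, completeness of data: data are rarely missing at random. A missing category, exclusion and imputation are named, and none is chosen, but "excluding those with missing data would not be a reasonable approach to analysis".
- Section 8.8: people with and without data might differ, for example those who died or were lost.

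**The concern.** The protocol foresees that some people will have no viral load near the time point and offers a remedy, but the remedy appears to be empty. What remains is a proportion that rests on people with an observed value, next to a statement that such data are unlikely to be missing at random.

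This touches the purpose of the study. Section 6.2 gives the effect of non-adherence on virologic failure as a main reason for doing it. Missed visits can plausibly lead both to late injections and to absent viral loads, so the people without a result may be those of most interest. If their number and status are not shown, a reader cannot tell a well-supported suppression figure from one that depends on who was tested.

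**Working it through.** **1. Does the fallback add anyone?** Let T be 6, 12 or 24 months. The window is T−6 to T+6 weeks. The fallback, read in the natural way, is T to T+6 weeks. The union of the two is T−6 to T+6 weeks, so nobody is added. Taken literally, the cap runs from the measurement itself, which sets no usable limit. A cap running from the end of the window (to T+12 weeks) would add people, but the text does not say that. In Aim 4 the fallback is uncapped and does reach past the window.

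**2. Does any stated analysis show the effect of people with no viral load?**

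| Stated element | What it does for them |
|---|---|
| Primary on-treatment analysis | Censors at last visit; assigns no outcome |
| Intent-to-treat sensitivity analysis | Lifts the discontinuation rule only; still needs a viral load |
| Sensitivity analysis in those with resistance data | Concerns another condition |
| Risk-factor models | Limited to people with enough follow-up |
| Completeness paragraph | Argues against exclusion; selects no method |

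Elsewhere in section 8.6 the protocol does describe such groups. It compares people with and without resistance tests, and people from clinics with a limit of detection above 50 copies/mL with those included. There is no counterpart for an absent viral load.

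**3. The plan's own precision figure.** Table 4 (section 8.4), N=500, P=0.05, so 25 events. The exact Clopper-Pearson limits are the 2.5% quantile of Beta(25, 476) and the 97.5% quantile of Beta(26, 475): 0.0326 and 0.0729. This reproduces the stated 0.033 to 0.073.

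**4. How far could missing results move it?** The missing share m is an assumption; the documents give none. With N=500, n measured and x failures (5% of n, rounded), the full-cohort proportion lies between x/N (no unmeasured person failed) and (x + N − n)/N (all did).

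| m | n | x | Exact CI among measured | Lower bound | Upper bound |
|---|---|---|---|---|---|
| 10% | 450 | 22 | 3.1% to 7.3% | 22/500 = 4.4% | (22+50)/500 = 14.4% |
| 20% | 400 | 20 | 3.1% to 7.6% | 20/500 = 4.0% | (20+100)/500 = 24.0% |

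The confidence interval hardly moves, while the bounds open widely. A milder assumption is that unmeasured people fail at r times the observed rate, giving (1−m)×5% + m×r×5%. For r = 2, 3 and 5 the result is 5.5%, 6.0% and 7.0% at m=10%, and 6.0%, 7.0% and 9.0% at m=20%.

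For suppression, 95% among those measured becomes 0.95×0.90 = 85.5% at m=10% or 0.95×0.80 = 76.0% at m=20% if no result counts as not suppressed.

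**5. Could m be that large?** If tests came at a fixed interval, unrelated to the start date, a 12-week window would hold a result for about 12/interval of people: 92% at 3-monthly (13.0 weeks), 69% at 4-monthly (17.4 weeks) and 46% at 6-monthly (26.1 weeks). Both the interval and the random timing are assumptions. Tests aimed at the 6-, 12- and 24-month dates would do better.

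**The case against.** Denominators, a no-result row and missing-data sensitivity analyses are commonly settled in the statistical analysis plan, which is not at hand. The protocol also admits the limitation in sections 8.6 and 8.8. Most of this stands for the denominator wording alone. It does not cover the fallback: the protocol fixes that rule itself, and as written it does nothing.

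The mechanism is also weaker than it first looks. Injections are given by a healthcare provider every one or two months, and under section 8.3.2 a missed injection without bridging beyond the allowed time counts as discontinuation. Many non-attenders therefore leave the on-treatment set and appear under Aim 2. The additional CRF collects data at 6, 12 and 24 months, so tests may cluster near those dates. Both points stand and argue for a smaller missing share than random timing gives. They do not show that it is negligible.

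A reader might infer that people without a result are dropped, and that the protocol thereby contradicts its own rejection of exclusion. The text does not support this. Dropping is stated nowhere, the sentence on exclusion concerns incomplete EuroSIDA variables in general, and a missing category or imputation stays open. Nor is the window expressly applied to VL <50 and <200; that link comes only from the Aim 3 heading.

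**Conclusion.** The point holds as a cheap improvement. The Aim 3 fallback adds nobody to the ±6-week window, VL <50 and <200 have no stated window, and no stated analysis shows what people without a viral load do to the result, although the protocol concedes that such gaps are unlikely to be random.

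A reader might go further and conclude that effectiveness will be overstated by a known amount. The documents do not allow that: they give neither a testing interval, a missing share nor a failure rate in the unmeasured. The bounds of 4.4% to 14.4% (10% missing) and 4.0% to 24.0% (20% missing), against 3.3% to 7.3% from sampling at N=500, assume 5% failure among those measured and are extremes. They show only that the unmeasured can matter more than sampling error. The N values in Table 4 are uptake scenarios, so a smaller evaluable number contradicts nothing.

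**What to change.** In sections 8.3.2 and 8.6:
- Apply the time-point window expressly to VL <50 and VL <200 as well as to failure.
- Correct the Aim 3 fallback so that it reaches beyond +6 weeks to a stated limit, and align its wording with Aim 4.
- Take as denominator at each time point everyone who started at least that long plus 6 weeks (or plus the fallback limit, if longer) before the data cut.
- Report no viral load in the window as its own category, split into still on treatment, stopped, and died or lost. The on-treatment estimate can stay beside it.
- Add two sensitivity analyses: no result counted as not suppressed, and the nearest result in a wider window, for example ±13 weeks. That span of 26 weeks would hold a test under roughly six-monthly testing. Because the 6- and 12-month windows then meet at about week 39 (26+13 = 52−13), each result should be assigned to one time point only.

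The cost is wording and some extra table rows, with no new data collection. The downside is a less favourable figure in one sensitivity analysis and a less exact time point in the other.
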